#### **Implementation**

All eligible participants who give consent will be randomized by the unblinded coordinator after completion of all baseline assessments. The randomization tool is only available to designated unblinded coordinators (UC) at each site. The UC will enter the required information in the tracking system, after which the participant's group assignment will be immediately available.

If the participant is randomized to the No Depression Screen arm, the UC will inform the participant that no further assessments are required.

If the participant is randomized to the Depression Screen and Notify arm, the UC will administer the PHQ-8. If the PHQ score is ≥ 10, the UC will notify the participant's primary care provider and/or cardiologist either through the tracking system, by email, or mail in accordance with their IRB requirements.

If the participant is randomized to the AHA Depression Screen, Notify, and Treat arm, the UC will administer the PHQ-8. IF the PHQ score is ≥ 10, the UC will inform the patient of the available treatment options. Depending on the participant's choice of treatment, the UC will facilitate the initial contact with the relevant treatment specialist(s), ideally within two weeks of randomization and will work closely with the treatment specialist(s) to monitor the participant's treatment progress. The participant's PCP and/or cardiologist will also be notified of the positive depression screen.

#### **Blinding**

The blinded coordinator (BC) will administer all study regular assessments at 6-, 12- and 18-months, and will not be allowed to know the participants' group allocation, and this is ensured by the "user-role" designation in the tracking system. In addition to the UC, and due to the nature of the study treatment, participants, site PIs, and other personnel not designated as BC, cannot be blinded to the group allocation, but are encouraged not to disclose the allocation either at or when assisting the BC in scheduling follow up assessments. After each study visit, the BC will complete a 1-item questionnaire asking if the participant disclosed if they were in treatment. This information will be tracked, however no intervention will occur if the BC becomes unblinded.

# **Data Collection, Management and Analysis**

#### **Data Collection Methods**

#### Screening

Screening will be accomplished in two stages. First, an EMR search of ICD-9 codes matched against the study eligibility and exclusion criteria will be used to identify eligible participants. The following ICD-9 discharge codes will be used to match eligibility criteria, 410 (acute myocardial infarction), 411 (unstable angina), 413.9 (angina pectoris NEC/NOS), 414 (coronary artery disease). Codes were updated for ICD-10 in later years of recruitment. Then, those who express interest will complete a short Screening Questionnaire to verify that none of the exclusion criteria apply to them.

#### **Baseline and Follow-Up Assessments**

Research data for the study include:

- Participants' responses to self-report assessments and measures including, demographics, CES-D10, quality of life (SF-12), symptoms checklist, health service use, and lost productivity, and unanticipated events
- Electronic medical record (EMR) data extraction

There will be four study visits/interviews: baseline, and three follow-up visits/interviews, at 6-, 12, and 18-months after enrollment. The list of forms and the schedule of collection is found in **Table 1** above. Personally identifiable information (PII) and protected health information (PHI) will be collected, and will be used to contact participants for follow-up visits, treatment delivery (if applicable), and to conduct a National Death Index search within 5 years after the study ends. Only authorized personnel, who have official status as part of the authorized research team, will have access to any records containing PII and PHI.

#### **Treatment-Related Information**

Study forms/guidelines are available to study treatment specialists to aid them in monitoring depressive symptoms, and tracking the progress of participants undergoing treatment. These forms are provided for the treatment specialists' convenience, and not for data analysis, and are included in the intervention manual.

#### **Healthcare Utilization Data**

Healthcare utilization data from date of enrollment to 18-months after will be downloaded from the integrated medical record systems at each site and delivered to Columbia University via secure electronic file transfer.

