#### **Interventions**

The 1500 participants who meet eligibility and indicate a willingness to participate and potentially receive treatment will then be randomized. Those randomized to the AHA Depression Screen, Notify & Treat or Depression Screen & Notify groups will then complete assessment of depressive symptom severity, while those randomized to No Depression Screen group will not. All participants will be followed according to the same schedule of assessments.

Overview of Visit Schedule & Measures. The overall guiding rationale for all visit and measure choices was to be cost-effective, brief, and convenient to the participant. The three participating health care organizations have different methods of recruiting however; they will all utilize an electronic medical record (EMR) algorithm to identify medically eligible patients. At the EMR eligibility stage, electronic medical records will be screened for documented ACS, age, language preference, and all other medical and psychiatric eligibility criteria. Patients identified as potentially eligible through this process may be contacted by mail, postcard, or email and offered either an email address or telephone number to contact if interested in study participation. This initial contact may include a study brochure, letter on behalf of their primary care provider, and/or a copy of the Informed Consent Form. Patients who express interest can either be screened and introduced to the consenting process over the phone, or scheduled for an in-person study screening and consent visit depending upon local practices and IRB approval.

In general, those who do respond by email or phone within approximately 2 weeks after the date of initial contact will be telephoned by the recruitment staff. We will carefully document who did not complete screening, who was ineligible (and for what reason) and who refused. Patients who consented and are eligible after screening will then be randomized during either the initial telephone call, a follow-up phone call or at an inperson visit. Participants who are randomized to Depression Screen & Notify arm will complete a PHQ-8 assessment, and those with clinically significant scores (≥ 10) will have a letter or electronic message sent to their PCP and/or cardiologist. Participants

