who are randomized to the AHA Depression Screen, Notify & Treat arm will also complete a PHQ-8 assessment, and those with clinically significant scores (≥ 10) will be offered the option of receiving treatment for their depressive symptoms. Participants will be presented with the option of receiving medication therapy (sertraline or bupropion), Cognitive Behavioral Therapy (delivered via phone), a combination of both therapies or neither therapy. Depending on their treatment choice, they will be scheduled for their initial treatment visit, ideally within two weeks of randomization. Their PCP and/or cardiologists will also be notified if they have clinically significant scores (≥ 10) on the PHQ-8 assessment. Those randomized to No Depression Screen group will not receive the depression screen PHQ-8 at baseline.

All participants, regardless of randomization assignment, will complete the CES-D10, SF-12 health-related quality of life measure, symptoms checklist and lost productivity at enrollment and after 6-, 12-, and 18-months of study participation. All participants will also complete the PHQ-8 assessment at 18-months, with referral to treatment for those with scores ≥ 10. Participants will be contacted by telephone, or have an in-person visit scheduled, as they prefer. These administration methods have been compared in past studies and found to be equivalent. These follow-up contacts will be brief, and scheduled at the participant's convenience wherever possible.

All participants will report their health service utilization at 6-, 12- and 18-months. Additionally, all will have EMR searches of health care utilization extracted for the 18-month duration of the trial.

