#### Overview of Cost/Health Care Utilization Data.

Costs to be collected for the trial	From electric medical record	From patient report
Antidepressant cost, therapy cost, other mental health visits	Х	X
Depression-free days		X
Primary care visits, ED/urgent care, other medical visits, diagnostic services, inpatient services other outpatient services	Х	
Days able to work/impact on work and leisure productivity		X

We will generate cost data using a combination of EMR extraction and patient surveys as detailed in the table above. We will calculate the cost of all possible depression care used (antidepressant cost and therapy cost. We will also collect data on all non-study delivery of depression treatment utilization from patient report and EMR. To derive other healthcare costs, we will use the EMR to collect data on all episodes of non-depression related healthcare utilization during the 18-month trial period: outpatient visits, ED/urgent care, as well as all in-patient care and any diagnostic tests or services. Average Medicare reimbursement rates according to diagnosis-related groups will be applied to inpatient visits to estimate hospitalization costs, and the Medicare fee schedule will be applied to outpatient and ED resource use according to current

procedural terminology codes. Finally, to calculate costs and potential cost-offsets from a societal perspective, we will collect participant report data on time lost from work. Lost productivity is believed by many experts to be assessed in our measure of health-related QoL instrument, the SF12. However, a sensitivity analysis will be conducted to test this assumption.

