# **Participant Timeline**

Table 1. Schedule of screening, baseline and follow-up forms

Form Name	Screening	Baseline	6 Months	12 Months	18 Months
Screening Questionnaire	X				
Subject Contact Information		Χ			
Subject Contact Information Update Form (if indicated)			Х	Х	Х
Demographics		Χ			
PHQ-8		Χ*			Х
CES-D10		Х	Х	Х	Х
SF-12		Χ	Χ	Χ	X
Health Service Use Questionnaire			Х	Х	Х
Symptoms Checklist		Χ	Χ	Χ	X
Lost Productivity Questionnaire		Χ	Χ	Χ	X
Unanticipated Event Report			۸	۸	٨
Quality Assurance Form**			Х	Х	X

\*Participants randomized to the No Depression Screen arm will NOT complete PHQ-8 at baseline

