#### **Hypothesis 2:**

Those randomized to AHA's Depression Screen, Notify & Treat intervention group will have a favorable incremental cost-effectiveness ratio when compared to No Depression Screen control group and also when compared to the Depression Screen & Notify control group.

For this hypothesis, we will judge the cost effectiveness of AHA Screen, Notify & Treat group compared to the Screen & Notify group, then we will compare the Screen & Notify group to the No Screen group on the basis of incremental cost-effectiveness ratios. The base case analysis will adopt a societal perspective with respect to costs and health benefits. Costs will include all healthcare costs and lost productivity cost related to use of website/staff time for depression screening, and the cost of all possible depression care used (antidepressant cost and therapy cost, including the cost for telephone/webcam use). Costs will be denominated in 2012 dollars and discounted at an annual rate of 3% as per the Panel on Cost-Effectiveness in Health and Medicine. For health benefits, we will convert SF-12 scores to QALYs, using the four (prerandomization, 6, 12, & 18 month) measured values. Incremental cost-effectiveness analyses for comparison of treatment groups will be calculated sequentially using the ratio of the difference in average cost per participant divided by the difference in average QALY gained.

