The other prespecified secondary outcome will be Health Care Costs and Lost Productivity. 1 At baseline, 6-months, 12-months, and 18-months, patients will report measures of economic productivity, including employment status, occupation, hours spent at work, and time lost from work for health-related reasons.11 At 6-months, 12-months, and 18-months, patients will also report healthcare utilization since their last intake assessment, including emergency department (ED) visits, hospitalizations (location, admission and discharge dates), psychiatric medication use, name and dose, ambulatory care visits with mental health specialists, cardiologists, as well as PCPs and finally hospitalizations for cardiovascular events. Patient self-reports of healthcare utilization will be supplemented by review of the EMR and claims systems to collect data on healthcare utilization during the 18-month trial period. Average Medicare reimbursement rates according to diagnosis-related groups will be applied to inpatient visits to estimate hospitalization costs, and the Medicare physician fee schedule will be applied to outpatient and ED resource use according to current procedural terminology codes. Costs of study depression treatment will also be incorporated into estimates of healthcare utilization costs for those assigned to the Screen, Notify, and Treat group who agree to depression treatment by study personnel. To estimate economic costs from a societal perspective, changes in productivity and time spent traveling to appointments will also be accounted for. Costs will be standardized across years using the U.S. Consumer Price Index and presented in U.S. dollars.12

-

¹Cost of health care utilization was erroneously listed as a co-primary outcome on the initial clinicaltrials.gov entry. This error was corrected in clinicaltrials.gov on October 25, 2017, prior to completion of data collection or any interim data analyses. As can be seen in the planned statistical analyses, the sample size for the study was driven entirely by the change in QALYs outcome. Cost-effectiveness analyses, in contrast, were never intended to be listed as a co-primary outcome as they were not guided by economic hypotheses involving statistical tests and sample size calculations for incremental cost-effectiveness ratios were never attempted.

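### The cost comparison uses no baseline information: it is an unadjusted difference in averages, and health-care use is collected only after enrollment, which gives up some precision on a secondary outcome

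*Protocol*

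**What the plan says.** Several places fix the window for health-care use, and they agree.

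- Protocol, Healthcare Utilization Data: "Healthcare utilization data from date of enrollment to 18-months after will be downloaded from the integrated medical record systems at each site".
- Protocol, Interventions: the records yield "EMR searches of health care utilization extracted for the 18-month duration of the trial", and "All participants will report their health service utilization at 6-, 12- and 18-months".
- Protocol, Overview of Cost/Health Care Utilization Data: "we will use the EMR to collect data on all episodes of non-depression related healthcare utilization during the 18-month trial period".
- SAP section 8: "At 6-months, 12-months, and 18-months, patients will also report healthcare utilization since their last intake assessment".
- Protocol, Participant Timeline, Table 1: the row "Health Service Use Questionnaire" is marked at 6, 12 and 18 months, with the baseline cell empty. Baseline and Follow-Up Assessments lists health service use among the research data but refers to Table 1 for timing.

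Lost productivity is collected at baseline as well as at follow-up (Table 1; SAP section 8).

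On analysis, Hypothesis 2 in the Protocol's Statistical Methods defines the ICER as the "ratio of the difference in average cost per participant divided by the difference in average QALY gained". It names no covariates, and SAP section 8 gives no model for cost. The introduction to Statistical Methods says randomization is stratified by study site. The Sensitivity Analysis section plans ICERs separately by health care system and simulation-based 95% intervals for cost and effectiveness.

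**The concern.** Cost is a prespecified secondary outcome and supplies the numerator of the ICER in Hypothesis 2. The primary outcome is referenced to each participant's own baseline utility, and SF-12, CES-D10, symptoms and lost productivity all have a baseline value. Health-care use does not, and the cost comparison does not use the baseline facts that the trial does hold.

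Cost varies between patients, and participants enter anywhere from 2 to 12 months after an ACS, so use before enrollment may predict use after it. If it does, leaving it out makes the interval for the cost difference wider than necessary and leaves chance imbalance uncorrected. The Protocol presents no power calculation for the ICER, so the design does not otherwise secure precision for cost. The by-site ICERs rest on smaller groups and are the most exposed.

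**Working it through.** **The plan's own figure.** No figure is stated for the cost comparison. The only sample-size figure is for QALYs: SD 0.17, difference 0.031, two-sided 5%, 80% power. n = 2 × (1.960 + 0.842)² × 0.17² / 0.031² ≈ 473 per group, against 475 stated, and 475 / 0.95 = 500. The figure reproduces. It is used below only as the arm size.

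**Formulas for cost.** Let r be the correlation between prior and later cost, in SD units of later cost.

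- Unadjusted SE of a pairwise difference = √(2/n). At n = 475 this is 0.0649, so the 95% half-width is 1.96 × 0.0649 = 0.127 SD.
- Adjustment for prior cost multiplies the variance by (1 − r²) and the SE by √(1 − r²). The equivalent unadjusted n is 475 / (1 − r²).
- If arms differ in prior cost by the 95% limit of chance, 0.127 SD, the unadjusted cost difference shifts by r × 0.127 SD.

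The documents do not give r, so it is an assumption shown as a range.

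| r | Variance cut | SE cut | 95% half-width (SD) | Equivalent n per arm | Shift from imbalance (SD) |
|---|---|---|---|---|---|
| 0.2 | 4% | 2% | 0.125 | 495 | 0.025 |
| 0.3 | 9% | 5% | 0.121 | 522 | 0.038 |
| 0.4 | 16% | 8% | 0.117 | 565 | 0.051 |
| 0.5 | 25% | 13% | 0.110 | 633 | 0.064 |

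**In dollars.** With an assumed SD of $10,000 and 500 per arm, SE = 10,000 × √(2/500) = $632. Multiplying by √(1 − r²) gives $620, $603, $580 and $548 for the four values of r.

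**By site.** With an assumed 100 per arm at one site, the 95% limit of chance imbalance is 1.96 × √(2/100) = 0.28 SD, about twice the whole-trial value. The shift is then 0.28 × r, or about 0.06 to 0.14 SD for r from 0.2 to 0.5. The site term drops out of a single-site analysis, so only patient-level covariates help there.

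**Limit on the gain.** Adjusting cost leaves the QALY uncertainty unchanged. The QALY SE at 500 per arm is 0.17 × √(2/500) = 0.0108. At an assumed $100,000 per QALY, ignoring any cost–QALY covariance, the SE of net benefit is √(1,075² + 632²) ≈ $1,247. It falls to √(1,075² + 548²) ≈ $1,207 at r = 0.5, about 3%. The plan specifies no net-benefit analysis; this only shows how the cost gain is diluted.

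**What already exists.** Site, ACS date (needed for eligibility) and baseline lost productivity are known for participants without any new extraction. Only prior health-care cost is missing. The documents give no basis for putting a number on the gain from the first three.

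**The case against.** The strongest reply is that nothing is broken. Allocation is randomized, the raw cost difference is a valid estimator, its sampling interval already reflects chance imbalance, and the Protocol says it had no economic hypotheses requiring statistical tests. All of that stands. It makes this a matter of efficiency.

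A reader might infer more than the documents support, in five ways.

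- That the cost difference is biased. It is not, because randomization protects it.
- That chance imbalance in prior cost carries over in full to the ICER. It carries over only in proportion to r.
- That different price levels at the health systems distort the comparison. Base-case use is priced at Medicare rates at all sites, actual system costs enter only in sensitivity analysis, and randomization is stated to be stratified by site.
- That nothing cost-related is measured before randomization. Lost productivity is. Current depression treatment is also an exclusion, so baseline depression-care cost should be small.
- That prior cost is available for the asking, because at the eligibility stage "electronic medical records will be screened for documented ACS, age, language preference, and all other medical and psychiatric eligibility criteria". That search matches diagnosis and discharge codes. Costing needs full utilization with procedure and DRG codes, and the documents do not say this is complete for the year before enrollment. A primary-care network and a medical center may not hold out-of-system care.

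It is also fair that r may be low. Every index ACS falls inside a 12-month look-back, and once that admission is removed the remaining prior cost may predict less.

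**Conclusion.** The point holds as a modest improvement to a secondary outcome. As planned, health-care use is collected only from enrollment, and the cost contrast uses no baseline information. The consequence is lost precision and less protection against chance imbalance, mainly in the by-site ICERs, and it applies to health-care cost only. It does not amount to bias, and it does not touch the primary QALY analysis.

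The size is illustrative. If r is 0.2 to 0.5, the variance of the cost difference falls 4% to 25% and its SE about 2% to 13%, with a smaller effect on any measure that combines cost with QALYs. Neither r nor a cost SD is in the documents, so the true gain could be at or below the low end.

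**What to change.** **Now, with data already held.** In SAP section 8, before unblinding, specify a regression estimate of the arm difference in cost adjusted for site, time since ACS and baseline lost productivity. State that this difference forms the ICER numerator, and keep raw means as a supporting analysis. The by-site ICERs would use the same model without the site term. The cost is SAP wording only.

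**Where authorization and record completeness allow.** In the Protocol's Healthcare Utilization Data section, extend the extraction to the 12 months before enrollment. Add prior health-care cost, excluding the index ACS admission, to the model. State in advance a functional form that handles zero costs and a rule for missing prior data. The cost is a wider data pull at each site and a check of consent and HIPAA authorization. The downside is that prior records may be incomplete at sites that do not capture out-of-system care. If completeness is poor, the first step stands on its own.

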#### **Data Management**

# Data Entry, Security and Storage

A dedicated, HIPAA-compliant, web-based tracking and data entry system created by KP-CHR will be used for this study. Baseline and follow-up self-report data will be collected in one of two ways: (1) the BC will complete the assessments with the participant over the phone or in-person, and will directly enter the responses on the web-based system, or (2) the blinded assessor completes the assessment using pen and paper forms, and either the BC or other research personnel will enter the data at a

later time. All data are stored in a secure server at Kaiser Permanente, and automatically backed up according to an established regular schedule.

